3.4.4 Handling of Missing Data and Outliers

3.4.4.1 Safety

Generally, no replacement will be done for Safety Missing Data and Outliers.

3.4.4.1.1 Immediate

For unsolicited systemic AEs, a missing response to the "Immediate" field is assumed to have occurred after the 30-minute surveillance period and will not be imputed.

3.4.4.1.2 Causal Relationship

By convention, all events reported at the injection site (either solicited or unsolicited) will be considered as related to the administered product and then referred to as reactions. In a same way, all solicited systemic events pre-listed in the CRF are also considered as related to vaccination and will be considered as reactions.

- For unsolicited systemic AE, missing relationship will be considered as related to study vaccine at the time of analysis.
- The missing relationship to study procedures for SAEs will not be imputed.

3.4.4.1.3 Intensity

For solicited reactions, missing intensities will be handled as described in Section 4.2.1.1.1. For unsolicited AEs, missing intensities will remain missing and will not be imputed.

3.4.4.1.4 Start Date and End Date

Missing or partially missing start dates or end dates for unsolicited AEs (including SAEs) will remain missing and not be imputed. If the start date is missing or partially missing, the time of onset will be considered to be missing. Nevertheless, unsolicited AEs with missing time of onset will be included in analyses within or not within the defined time window (according to the section 4.2.1.2.4), according to the last vaccination (computed according to the section 4.2.1.2.3). If either the start date or end date is missing or partially missing, the duration will be considered missing.

Missing or partially missing end dates for ongoing solicited AEs will remain missing and not be imputed.

3.4.4.1.5 Action Taken

Missing actions taken will remain missing and not be imputed.

3.4.4.2 Immunogenicity

No imputation of missing values and no search for outliers will be performed. LLOQ and ULOQ management will be performed as described in Section 4.2.3.1.

3.5 Interim Analysis

No analyses are planned to be performed prior to the formal completion of the study.

3.6 Data Monitoring Committee (DMC)

Not applicable.

4 Complementary Information on Assessment Methods

Study assessments and procedures are detailed in Section 8 of the protocol. This section focusses on complementary/additional information not detailed in the protocol.

4.1 Complementary Information for Endpoints Assessment Methods

Subgroup Analysis

Additional subgroup analyses by age categories (12 Months-23 Months, Children 2 to 9 years of age, Adolescents 10 to 17 years of age, Adults 18 to 55 years of age and older adults 56 years and above) for immunogenicity and safety parameters for all populations analysis sets.

The following parameters will be assessed before and 30 days after the vaccination:

- hSBA seroprotection rate (titer ≥ 1:8) and 95% CI
- GMTs with 95% CI
- Percentage of participants with titer $\geq 1:4$ and 95% CI
- Percentage of participants with hSBA vaccine seroresponse and 95% CI
- Percentage of participants with titers ≥ 4-fold rise from pre-vaccination to post-vaccination, and 95% CI

The safety overview will be also described by age subgroups.

4.1.1 Definition of enrolled participants

Enrolled study participants are study participants that had their eligibility evaluation and passed screening. For this study only enrolled participants will be analyzed.

4.1.2 Sensitivity Analysis due to Blood Sample Issues

If more than 10% participant had blood samples not suitable for use. Then additional immunogenicity sensitivity analyses will be performed for subjects with blood samples handled incorrectly during collection, processing, storage or shipment, and may have potential impact on the analysis results (eg, blood samples stored out of temperature after a power outage) based on the PPASs. The outputs will be provided in Appendix 15 of the CSR.

The following immunogenicity parameters will be assessed:

- hSBA seroprotection rate (titer ≥ 1:8) and 95% CI
- GMTs with 95% CI
- Percentage of participants with titer ≥ 1:4 and 95% CI
- Percentage of participants with hSBA vaccine seroresponse and 95% CI
- Percentage of participants with titers \geq 4-fold rise from pre-vaccination to post-vaccination, and 95% CI

4.2 Complementary Information on Derived Endpoints: Calculation Methods

4.2.1 Safety

4.2.1.1 Solicited Reactions

4.2.1.1.1 Daily Intensity

All daily records for solicited reactions will be derived into daily intensity according to the following classification: None, Grade 1, Grade 2, Grade 3, or Missing (Unknown).

For the derivation of daily intensities, the following sequential steps will be applied:

- 1. Solicited reactions (except Fever/Pyrexia) with CRF presence recorded as "No" and with all daily records missing (Unknown) then all daily intensities will be derived as None.
- 2. For non-measurable solicited reactions, daily intensities will correspond to daily records reported in the clinical database. For measurable solicited reactions the daily measurements reported in the clinical database will be converted based upon the intensity scales defined in the protocol; this assumes a reaction that is too large to measure (non-measurable, "NM") is Grade 3. Note the intensity could be considered "None" (not a reaction) in the analysis despite being considered a reaction by the investigator (e.g., swelling measurement > 0 mm but < 25 mm in adults).

Note: The maximum intensity on the ongoing period is derived from the record of the maximum intensity/measurement after the end of the solicited period following the rule described above.

Table 4.1: Solicited injection site reactions: terminology, definitions, and intensity scales – Infants and toddlers aged ≤ 23 months

CRF term (MedDRA	Injection site tenderness	Injection site erythema	Injection site swelling
lowest level			
term [LLT])			
Diary card	Tenderness	Redness	Swelling
term			
Definition	mobilized	including the approximate point of needle entry	Swelling at or near the injection site Swelling or edema is caused by a fluid infiltration in tissue or cavity and, depending on the space available for the fluid to disperse, swelling may be either soft (typically) or firm (less typical) to touch and thus can be

			best described by looking at the
			size of the swelling
Intensity	Grade 1: Minor reaction when	Grade 1: > 0 to < 25 mm	Grade 1: > 0 to < 25 mm
scale*	injection site is touched	Grade 2: \geq 25 to	Grade 2: \geq 25 to \leq 50 mm
	Grade 2: Cries or protests	< 50 mm	Grade $3: \ge 50 \text{ mm}$
	when injection site is touched	Grade $3: \ge 50 \mathrm{mm}$	
	Grade 3 (CRF): Cries when		
	injected limb is mobilized, or		
	the movement of the injected		
	limb is reduced		
	Grade 3 (diary card): Cries		
	when injected limb is moved		
	or the movement of the		
	injected limb is reduced		

^{*} For tenderness, the scale will be provided in the CRF and the intensity will be transcribed from the diary card. For other injection site reactions (erythema and swelling), the classification as Grade 1, 2, or 3 will be applied at the time of statistical analysis; the scale is provided for information purposes only. The actual size of the reaction will be reported in the CRF.

Table 4.2 : Solicited injection site reactions: terminology, definitions, and intensity scales – Children aged 2 through 11 years

CRF term (MedDRA lowest level term [LLT])	Injection site pain	Injection site erythema	Injection site swelling
Diary card	Pain	Redness	Swelling
term Definition	Pain either present spontaneously or when the injection site is touched or injected limb is mobilized	Presence of a redness including the approximate point of needle entry	Swelling at or near the injection site Swelling or edema is caused by a fluid infiltration in tissue or cavity and, depending on the space available for the fluid to disperse, swelling may be either soft (typically) or firm (less typical) to touch and thus can be best described by looking at the size of the swelling
Intensity scale*	CRF: Grade 1: Easily tolerated Grade 2: Sufficiently discomforting to interfere with normal behavior or activities Grade 3: Incapacitating, unable to perform usual activities Diary card: Grade 1: No interference with usual activities Grade 2: Some interference with usual activities Grade 3: Significant; prevents usual activities	Grade 1: > 0 to < 25 mm Grade 2: $\ge 25 \text{ to}$ < 50 mm Grade 3: $\ge 50 \text{ mm}$	Grade 1: > 0 to < 25 mm Grade 2: \geq 25 to < 50 mm Grade 3: \geq 50 mm

^{*} For pain, the scale will be provided in the CRF and the intensity will be transcribed from the diary card. For other injection site reactions (erythema and swelling), the classification as Grades 1, 2, or 3 will be applied at the time of statistical analysis; the scale is provided for information purposes only. The actual size of the reaction will be reported in the CRF.

Table 4.3 : Solicited injection site reactions: terminology, definitions, and intensity scales – Adolescents and adults aged \geq 12 years

CRF term (MedDRA lowest level term [LLT])	Injection site pain	Injection site erythema	Injection site swelling
Diary card term	Pain	Redness	Swelling
Definition	Pain either present spontaneously or when the injection site is touched or injected limb is mobilized	redness including	Swelling at or near the injection site Swelling or edema is caused by a fluid infiltration in tissue or cavity and, depending on the space available for the fluid to disperse, swelling may be either soft (typically) or firm (less typical) to touch and thus can be best described by looking at the size of the swelling
Intensity scale*	CRF: Grade 1: A type of adverse event that is usually transient and may require only minimal treatment or therapeutic intervention. The event does not generally interfere with usual activities of daily living. Grade 2: A type of adverse event that is usually alleviated with additional therapeutic intervention. The event interferes with usual activities of daily living, causing discomfort but poses no significant or permanent risk of harm to the research participant. Grade 3: A type of adverse event that interrupts usual activities of daily living, or significantly affects clinical status, or may require intensive therapeutic intervention. Diary card: Grade 1: No interference with usual activities Grade 2: Some interference with usual activities	Grade 1: ≥25 to ≤50 mm Grade 2: ≥51 to ≤100 mm Grade 3: >100 mm	Grade $1: \ge 25$ to ≤ 50 mm Grade $2: \ge 51$ to ≤ 100 mm Grade $3: > 100$ mm

Grade 3: Significant; prevents usual	
activities	

Table 4.4 : Solicited systemic reactions: terminology, definitions, and intensity scales – Infants and toddlers aged \leq 23 months

CRF term	Fever	Vomiting	Crying	Drowsiness	Appetite lost	Irritability
(MedDRA			abnormal			
lowest level						
term						
[LLT])						
Diary card	Temperature	\mathcal{C}		Drowsiness	Loss of	Irritability
term			crying		appetite	
Definition	Elevation of			Reduced	-	An excessive
			crying without		scale	response to
	≥38.0°C	include		surroundings,		stimuli:
		spitting up		or increased		increased
				sleeping		fussiness,
						whining, and
						fretfulness
						despite
						attempts to
						comfort the
						infant and
						despite
						caregiver
						responses that
						would normally
						be soothing
			Grade 1:	Grade 1:	Grade 1:	Grade 1: Easily
scale*	\geq 38.0°C to	1 episode per		Sleepier than	Eating less	consolable
	≤38.5°C	24 hours		usual or less	than normal	
				interested in		
				surroundings		
				Grade 2: Not	Grade 2:	Grade 2:
		5 episodes per		interested in	Missed 1 or 2	1 0
	≤39.5°C	24 hours		surroundings or		increased
				did not wake	completely	attention
				up for a feed /		
				meal		

^{*} For pain, the scale will be provided in the CRF and the intensity will be transcribed from the diary card. For other injection site reactions (erythema and swelling), the classification as Grades 1, 2, or 3 will be applied at the time of statistical analysis; the scale is provided for information purposes only. The actual size of the reaction will be reported in the CRF.

Grade 3:	Grade 3:	Grade 3:	Grade 3:	Grade 3:	Grade 3:
> 39.5°C	≥6 episodes	> 3 hours	Sleeping most	Refuses ≥ 3	Inconsolable
	per 24 hours		of the time or	feeds / meals	
	or requiring		difficult to	or refuses	
	parenteral		wake up	most feeds/	
	hydration			meals	

Table 4.5 : Solicited systemic reactions: terminology, definitions, and intensity scales – Children aged 2 through 11 years, adolescents or adults aged \geq 12 years

CRF term (MedDRA lowest level term [LLT])	Fever	Headache	Malaise	Myalgia
Diary card term	Temperature	Headache		Muscle aches and pains
Definition	Elevation of temperature to ≥°38.0°C	Pain or discomfort in the head or scalp. Does not include migraine.	Malaise is a generalized feeling of discomfort, illness, or lack of well-being that can be associated with a disease state. It can be accompanied by a sensation of exhaustion or inadequate energy to accomplish usual activities.	than one muscle at the same time. Muscle pain can also
Intensity scale*	≤38.4°C	CRF: Grade 1: A type of adverse event that is usually transient and may require only	CRF: Grade 1: A type of adverse event that is usually transient and	CRF: Grade 1: A type of adverse event that is usually transient and may require only

^{*} For all reactions (except fever), the scale will be provided in the CRF and the intensity will be transcribed from the diary card. For fever, the body temperature will be recorded, and the classification as Grade 1, 2, or 3 will be assigned at the time of the statistical analysis based on the unit used to measure the temperature and the intensity scale.

	minimal treatment or	minimal treatment or	minimal treatment or
		therapeutic	therapeutic
	therapeutic intervention. The	intervention. The	intervention. The
	event does not	event does not	event does not
	generally interfere	generally interfere	generally interfere
	with usual activities	with usual activities	with usual activities
G 1 2 2 20 50G	of daily living.	of daily living.	of daily living.
Grade 2: ≥ 38.5 °C to	Grade 2: A type of	Grade 2: A type of	Grade 2: A type of
≤38.9°C	adverse event that is	adverse event that is	adverse event that is
	usually alleviated	usually alleviated	usually alleviated
	with additional	with additional	with additional
	therapeutic	therapeutic	therapeutic
	intervention. The	intervention. The	intervention. The
		event interferes with	event interferes with
	usual activities of	usual activities of	usual activities of
	daily living, causing	daily living, causing	daily living, causing
	discomfort but poses	discomfort but poses	discomfort but poses
	no significant or	no significant or	no significant or
	permanent risk of	permanent risk of	permanent risk of
	harm to the research	harm to the research	harm to the research
	participant.	participant.	participant.
Grade $3: \ge 39.0$ °C	Grade 3: A type of	Grade 3: A type of	Grade 3: A type of
	adverse event that	adverse event that	adverse event that
	interrupts usual	interrupts usual	interrupts usual
	activities of daily	activities of daily	activities of daily
	_	living, or	living, or
	significantly affects	significantly affects	significantly affects
			clinical status, or may
	require intensive	require intensive	require intensive
	therapeutic	therapeutic	therapeutic
	intervention.	intervention.	intervention.
	Diary card:		Diary card:
	Grade 1: No	Grade 1: No	Grade 1: No
	interference with	interference with	interference with
	usual activities	usual activities	usual activities
	Grade 2: Some	Grade 2: Some	Grade 2: Some
	interference with	interference with	interference with
	usual activities	usual activities	usual activities
	Grade 3: Significant;	Grade 3: Significant;	Grade 3: Significant;
	prevents usual	prevents usual	prevents usual
		activities	 
	activities	acuvines	activities

^{*} For all reactions (except fever), the scale will be provided in the CRF and the intensity will be transcribed from the diary card. For fever, the body temperature will be recorded, and the classification as Grade 1, 2, or 3 will be assigned at the time of the statistical analysis based on the unit used to measure the temperature and the intensity scale.

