4.2.1.1.3 Presence

Presence is derived from the maximum overall intensity over the time period considered:

- None: No presence
- Grade 1, Grade 2, or Grade 3: Presence
- Missing or Unknown: Missing presence

Participants with at least one non-missing presence for a specific endpoint will be included in the analysis. Conversely, those without a non-missing presence will not be included in the analysis of the endpoint.

The time period is displayed as D1-D4, D5-D8, D9 and later.

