4.2.1.2 Unsolicited AEs

4.2.1.2.1 Presence

An observation will be considered an event if it has at least a verbatim term and is not a Grade 0 intensity event.

Grade 0 events are not included in safety analysis but are included in separate listings.

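### A solicited reaction recorded as present in the CRF but with no daily grade is dropped from its endpoint, while the matching absent record is kept, so some reaction rates are understated whenever such records occur

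*SAP*

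**What the plan says.** SAP 4.2.1.1.1 derives daily intensity in two sequential steps. The first covers all solicited reactions except fever, namely those "with CRF presence recorded as 'No' and with all daily records missing (Unknown) then all daily intensities will be derived as None". The second covers everything else. "For non-measurable solicited reactions, daily intensities will correspond to daily records reported in the clinical database", and measured reactions are converted to grades from their size, with one too large to measure set to Grade 3.

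Section 4.2.1.1.3 does not return to the CRF item: "Presence is derived from the maximum overall intensity over the time period considered". A missing maximum gives a missing presence. "Conversely, those without a non-missing presence will not be included in the analysis of the endpoint".

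The missing-data sections add no further rule. SAP 3.4.4.1.3 points back: "For solicited reactions, missing intensities will be handled as described in Section 4.2.1.1.1". SAP 3.4.4.1 states the default: "Generally, no replacement will be done for Safety Missing Data and Outliers".

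For unsolicited AEs, SAP 4.2.1.2.1 needs no grade: "An observation will be considered an event if it has at least a verbatim term and is not a Grade 0 intensity event".

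**The concern.** The safety endpoint is the presence of each solicited reaction. For a subjective reaction such as headache, malaise or irritability, a CRF answer of Yes settles presence even when the grade is unknown. The SAP accepts the negative answer without grades and discards the positive one. A known reactor leaves both numerator and denominator, while a known non-reactor with the same empty daily grid stays.

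This goes against the SAP's approach elsewhere. An ungraded unsolicited AE still counts. A missing relationship is taken as related (3.4.4.1.2). An unsolicited AE with a wholly missing start date is placed within 30 days (4.2.1.2.4). For discontinuations, section 4.2.2.6 counts an unsolicited AE whose grade is missing but requires at least Grade 1 for a solicited one.

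The study exists to supply local immunogenicity and safety data for registration in Vietnam (protocol 2.1), and reactogenicity rates are a main part of that. Some age subgroups may hold as few as 20 participants, where one or two records move a percentage visibly.

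**Working it through.** **The plan's own figures.** The documents give no figure for this rule. Their only safety precision statement, in SAP 3.2, reproduces: 1 − (1 − 0.0075)^400 = 95.1% and 1 − (1 − 0.015)^200 = 95.1%. It concerns seeing at least one event and does not bear on this point.

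**Tracing the rules when every daily record is missing (fever excepted)**

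| CRF presence | Daily intensity (4.2.1.1.1) | Maximum (4.2.1.1.2) | Presence (4.2.1.1.3) | In the endpoint? |
|---|---|---|---|---|
| No | None, by step 1 | None | No presence | Yes, as non-reactor |
| Yes | Missing; no step applies | Missing | Missing | No |

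Fever is outside step 1, so this asymmetry does not affect it.

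**Size where a Yes is a reaction.** This covers the non-measurable reactions, and erythema and swelling under 12 years, where any size above 0 mm is at least Grade 1 (SAP Tables 4.1 and 4.2). Let N be the participants, r the true reactors and k the reactors with CRF Yes and no daily grade. All non-reactors are kept.

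True rate = r/N. Reported rate = (r − k)/(N − k).

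Inputs: N = 223 is the planned enrolment per age category (SAP 3.2); r = 67 and k are assumptions.

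| k | Reported | Shift from 67/223 = 30.0% |
|---|---|---|
| 0 | 67/223 = 30.0% | none |
| 1 | 66/222 = 29.7% | −0.3 points |
| 2 | 65/221 = 29.4% | −0.6 points |
| 5 | 62/218 = 28.4% | −1.6 points |
| 10 | 57/213 = 26.8% | −3.3 points |

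At the minimum subgroup size (N = 20, assumed r = 6, so 30.0%), k = 2 gives 4/18 = 22.2%.

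In general, with true rate p and a share m of reactors ungraded, the reported rate is p(1 − m)/(1 − pm):

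| True rate | m = 5% | m = 10% | m = 20% |
|---|---|---|---|
| 10% | 9.55% | 9.09% | 8.16% |
| 20% | 19.19% | 18.37% | 16.67% |
| 40% | 38.78% | 37.50% | 34.78% |

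**Erythema and swelling at 12 years and over.** Grade 1 starts at 25 mm (SAP Table 4.3), and 4.2.1.1.1 notes that a smaller reaction is analysed as None even if the investigator called it a reaction. Assume 20 of 190 graded participants reach 25 mm and 10 more are CRF Yes with no measurement. The SAP reports 20/190 = 10.5%. The full rate is:

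- 20/200 = 10.0% if none of the 10 reached 25 mm
- 25/200 = 12.5% if half did
- 30/200 = 15.0% if all did

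The reported rate is too low only if the dropped participants reach 25 mm more often than the 10.5% seen among those kept.

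**The case against.** The strongest reply is that such a record should be uncommon. Protocol 10.2.5 requires an intensity grade for each AE. Protocol 8.3.2 has the investigator interview participants or parents and try to clarify incomplete diary entries, and protocol 10.1.7 provides for source data verification. One graded day is enough for presence, so the gap needs every day of D01 to D08 to be blank in someone recorded as Yes. A reaction too large to measure is not lost either, since it becomes Grade 3. This stands as a reason to expect small counts, but it does not make them zero. The diary is reviewed only at Visit 2 (D31 to D45), more than three weeks after the solicited period ends. The two telephone calls, as described, ask about SAEs and give reminders; they do not collect grades. A lost diary with a recalled reaction would produce this record.

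A second reply is that blank grades are natural when presence is No, so step 1 is sensible. That is right. The defect is the missing counterpart for Yes, not step 1. It also means that use of the No rule says nothing about how often the Yes case arises.

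Third, the shifts are small beside the sampling error. The Clopper-Pearson 95% interval is 24.1% to 36.5% for 67/223 and 11.9% to 54.3% for 6/20, and no hypothesis is tested. This limits the consequence, but a systematic omission is not covered by a confidence interval.

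Fourth, the SAP deliberately defines presence from graded intensity and lets a measurement override the investigator's view. That explains erythema and swelling at 12 years and over. It does not explain a non-measurable reaction, where there is no measurement to prefer.

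**Conclusion.** The gap is real. As written, the SAP removes a participant recorded as having the reaction when no daily grade exists, and keeps the matching participant recorded as not having it. Whenever this happens, the rates of non-measurable solicited reactions, and of erythema and swelling under 12 years, are understated.

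A reader might infer that every rate except fever is biased downward, or that the rule can never raise a rate. The documents do not support either. A reaction with no such record has no bias. At 12 years and over, dropping erythema or swelling below 25 mm can raise the rate, as the 10.5% against 10.0% example shows.

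The size rests on assumed counts. At a true rate near 30% in 223 participants, one or two such records cost 0.3 to 0.6 percentage points, and ten cost about 3.3. Given the data-collection procedures, the lower end is more plausible, though small subgroups are more exposed. The change should be made because it is cheap and brings solicited reactions into line with how the SAP treats ungraded unsolicited AEs.

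**What to change.** Add to SAP 4.2.1.1.1 and 4.2.1.1.3:

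- For non-measurable reactions, and for erythema and swelling under 12 years, CRF presence Yes with all daily records missing is analysed as presence with maximum intensity missing. The participant is in the numerator and denominator and appears in a grade-missing row.
- For erythema and swelling at 12 years and over, presence stays missing, and the number of such participants is reported with the table.

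The condition should follow the grading scale that applies to the participant, because the 10 to 17 year analysis subgroup spans both scales.

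The cost is a short addition to the SAP and one programming condition on a field already collected. Reported rates may rise slightly, and the tables gain one row. If no such records exist, the rates do not change.

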3.4 Statistical Analyses

3.4.1 General Considerations

Safety and immunogenicity parameters will be analyzed in specified analysis sets in the overall population, as well as by age categories (12 months -23 months, ≥ 24 months).

The statistical analyses will be performed under the responsibility of the Sponsor's Biostatistics platform using SAS® Version 9.4 or later.

For descriptive purposes, the following statistics will be presented:

Table 3.1: Descriptive statistics produced

Disposition and follow-	Categorical data	Number of participants.		
up description		Percentage of participants.		
	Continuous data	Mean, standard deviation, quartiles, minimum and		
		maximum.		
Baseline characteristics	Categorical data	Number of participants.		
		Percentage of participants.		
	Continuous data	Mean, standard deviation, quartiles, minimum and		
		maximum.		
Clinical safety results	Categorical data	Solicited: Number and percentage (95% CIs for		
		main endpoints) of participants.		
		Unsolicited: Number and percentage (95% CIs for		
		main endpoints) of participants and number of		
		events.		
Immunogenicity results	Categorical data	Number and percentage (95% CIs for main		
	(seroprotection,	endpoints) of participants.		
	seroconversion, cutoff)			
	Continuous data	Log10: Mean and standard deviation.		
	(titer / data†)	Anti-Log10 (work on Log10 distribution, and anti-		
		Log10 applied): Geometric mean, 95% CI of the		
		geometric mean, quartiles, minimum, and		
		maximum.		
		Graphical representation by Reverse Cumulative		
		Distribution Curve (RCDC).		

The confidence interval (CI) for the single proportion will be calculated using the exact binomial method (Clopper-Pearson method), quoted by Newcombe (1), i.e., using the inverse of the beta integral with SAS®.

For immunogenicity results, assuming that Log10 transformation of the titers / data follows a normal distribution, at first, the mean and the 95% CI will be calculated on Log10 (titers / data) using the usual calculation for normal distribution (using Student's t distribution with n-1 degree of freedom), then antilog transformations will be applied to the results of calculations, in order to provide geometric means (GMs) and their 95% CI.

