3.4.3 Safety Endpoint

No statistical hypotheses will be tested.

Safety results will be described for participants in the study. The main parameters for the safety endpoints will be described by 95% CIs (based on the Clopper-Pearson method).

Depending on the items, the endpoints recorded or derived could include: nature (Medical Dictionary for Regulatory Activities [MedDRA] preferred term), time of onset, duration/number of days of occurrence, intensity, relationship to the vaccine, whether the AE led to early termination from the study, outcome, and seriousness criterion.

All safety analyses will be performed on the SafAS.

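### Rows that cross age 12 pool two definitions of erythema and swelling (> 0 mm below 12, >= 25 mm from 12), with no common-size row to read them by

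*SAP*

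**What the plan says.** SAP 4.2.1.1.1 (Daily Intensity) gives the rule for erythema and swelling: "For measurable solicited reactions the daily measurements reported in the clinical database will be converted based upon the intensity scales defined in the protocol". Three scales follow it and match protocol Tables 10.1 to 10.3.

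- Up to 23 months (Table 4.1) and "Children aged 2 through 11 years" (Table 4.2): Grade 1 starts above 0 mm, Grade 2 at 25 mm and Grade 3 at 50 mm.
- From 12 years (Table 4.3): Grade 1 starts at 25 mm, and Grade 3 lies above 100 mm.

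SAP 4.2.1.1.3 makes presence follow the grade: "Grade 1, Grade 2, or Grade 3: Presence". The SAP says openly that a swelling under 25 mm in an adult may be analysed as no reaction.

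SAP 3.4.1 reports safety in the overall population, "as well as by age categories (12 months -23 months, ≥ 24 months". SAP 3.4.3 adds intervals: "The main parameters for the safety endpoints will be described by 95% CIs (based on the Clopper-Pearson method". SAP 4.1 adds five age groups: "Additional subgroup analyses by age categories (12 Months-23 Months, Children 2 to 9 years of age, Adolescents 10 to 17 years of age", then adults 18-55 and older adults from 56. Their scope is "for immunogenicity and safety parameters for all populations analysis sets", but the parameters listed are immunogenicity parameters, and for safety the only output named is this: "The safety overview will be also described by age subgroups".

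**The concern.** No reporting boundary lies at 12 years, where the definition of a reaction changes. A 20 mm swelling is a reaction at age 11 and none at age 12. Three rows therefore combine two definitions of the same endpoint: overall, >= 24 months and 10-17 years. Their percentages depend on how large reactions are, but also on how many participants happened to be under 12. The same holds for Grade 3 (50 mm or more against more than 100 mm).

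What is at stake is interpretation. A pooled percentage with an exact interval looks like the rate of one event. Someone who sets the 12-23 months row beside the >= 24 months row could take part of a scale difference for an age difference. The SAP's note on adult swellings explains how one participant is graded. It does not say that a pooled row mixes two thresholds, or in what proportion. No row at a common size is planned, although the size is recorded in the CRF and grading is applied only at analysis.

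**Working it through.** The plan gives no figure on this point, so there is none to reproduce. The check is how far the scale alone can move a row.

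**Inputs from the documents.** The thresholds and the presence rule are as above. Each of the two main age categories enrols 223. Within the >= 24 months category, each of four subgroups has a minimum of 20 (protocol 1.1, Number of Participants).

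**Assumptions, not in the documents.** Reaction sizes have the same distribution at every age. P0 is the probability of any size above 0 mm, and P25 the probability of 25 mm or more. The >= 24 months mix is near even: four groups of about 56, with 2 of the 8 single years in the 10-17 group being ages 10-11. That puts 56 + 14 = 70 participants under 12, so w = 70/223 = 0.314.

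**Formulas.**

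- Rate in the >= 24 months row = w x P0 + (1 - w) x P25.
- Rate in the 12-23 months row = P0.
- Scale-only gap between them = (1 - w) x (P0 - P25).
- Overall = the mean of the two rows, since both have 223.

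**Results.**

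| P0 / P25 | 12-23 months | >= 24 months | Gap (points) | Overall |
|---|---|---|---|---|
| 20% / 5% | 20.0% | 0.314 x 20 + 0.686 x 5 = 9.7% | 0.686 x 15 = 10.3 | 14.9% |
| 10% / 2% | 10.0% | 0.314 x 10 + 0.686 x 2 = 4.5% | 0.686 x 8 = 5.5 | 7.3% |
| 10% / 8% | 10.0% | 0.314 x 10 + 0.686 x 8 = 8.6% | 0.686 x 2 = 1.4 | 9.3% |

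A single >= 25 mm rule would give P25 in every row, whatever the mix. In the 10-17 years row, with a quarter aged 10-11, 20%/5% gives 0.25 x 20 + 0.75 x 5 = 8.8%.

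**Bounds on the mix.** The enrolment minimums alone allow w from 20/223 = 9.0% to 183/223 = 82.1%. At 20%/5% that is 6.3% to 17.3% in the >= 24 months row and 13.2% to 18.7% overall. These are limits only; the trial will report one actual mix.

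**What planned tables could recover.** Below 12, Grade 2 or higher means 25 mm or more. From 12, any presence means 25 mm or more. If solicited reactions are tabulated by grade in the five SAP 4.1 groups, a common >= 25 mm count follows for 12-23 months, 2-9, 18-55 and >= 56 years. In the 10-17 years group, Grade 1 mixes sizes under 25 mm at ages 10-11 with sizes of 25 to 50 mm at ages 12-17. On the mix above and 20%/5%, the unresolved part is 14 x 0.15 = 2.1 participants, or 2.1/223 = 0.9 points of the >= 24 months row. A common reading at > 0 mm could not be rebuilt, because sizes under 25 mm from age 12 drop out of every graded summary.

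**The case against.** The strongest reply is that nothing inferential depends on this. The study is uncontrolled, has a single group and tests no hypothesis. A reader might infer that a planned comparison of toddlers with older participants is biased. The documents do not support that: SAP 3.4.1 lists age categories for description and plans no contrast between them. The solicited terms differ too (tenderness against pain, for example), so the two rows were never fully like for like. This part of the reply stands.

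A reader might also infer that the scales are a mistake, or that the SAP departs from the protocol. Neither holds. The convention is the protocol's own, the SAP follows it, and its effect on small adult reactions is stated.

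A third reply is that the five subgroups already resolve the matter. That is largely true if SAP 4.1 means solicited reactions tabulated by grade; the remainder is then Grade 1 at ages 10-11. However, SAP 4.1 spells out only the safety overview, and no table shells are in the documents, so the mitigation is possible but not assured.

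Finally, the illustration rests on assumed rates. That is correct, and if few reactions measure under 25 mm the effect is small, as the 10%/8% case shows.

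**Conclusion.** The point holds as a matter of presentation. Followed as written, the overall, >= 24 months and 10-17 years rows combine two definitions of erythema and swelling, and no common-size row is planned. The definitions and the pooling come straight from the text. That these rows will appear for the two reactions is inferred from SAP 3.4.1 and 4.1.

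The size cannot be known from the documents. The 1.4 to 10.3 point range depends on equal sizes at all ages, on 70 of 223 under 12 and on the chosen rates. It shows that the effect may be trivial or visible; it does not forecast a result. The stronger conclusion, that the mixing can never be undone, is not supported: with graded subgroup tables most of a >= 25 mm reading can be recovered. No test, sample size or decision rule is touched. This is a cheap improvement.

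**What to change.** Keep the age-specific grading. Then take one of two routes for erythema and swelling.

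- In the overall, 12-23 months, >= 24 months and 10-17 years rows, add the number and percentage of participants with any size of 25 mm or more, taken from the CRF measurement. Count a reaction recorded as too large to measure (NM) as 25 mm or more.
- Or tabulate these two reactions by scale group: 12-23 months, 2-11 years, and 12 years and above.

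With either route, footnote the pooled rows with the two thresholds and the numbers of participants under 12 and aged 12 or over.

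The cost is a sentence in the SAP, a footnote and a few extra table rows. No new data are needed.
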